4.4 END OF STUDY DEFINITION

A participant is considered to have completed the study if he or she has completed all phases of the study including the last visit or the last scheduled procedure shown in Section 1.3 and Figure 1.

5 STUDY POPULATION

5.1 INFORMED CONSENT

An informed consent, written in accordance with the Declaration of Helsinki will be obtained from each participant before commencing any trial-related activities. The person/physician responsible for recruitment will explain the nature, purpose and potential risks of the study and will provide the participant with a copy of the signed informed consent.

5.2 INCLUSION CRITERIA

In order to be eligible to participate in this study, an individual must meet all of the following criteria:

1. Participants are 18 – 70 years of age inclusive
2. Participant is in generally good health, as determined by the investigator
3. Participant is willing and able to individually complete written informed consent and agrees to comply with all study related testing and examinations
4. Participant must be geographically stable (e.g., expects to be available and capable of returning for all study specified test and examinations) during the study period
5. Participant has been diagnosed with T1DM for at least 12 months
6. C-peptide <0.6 nmol/L at screening
7. Participant has been using insulin pump therapy for at least 6 months and is currently using a Medtronic MiniMed pump, model series 530 or higher. Use of 670G in auto mode is acceptable.
8. Participant can provide a minimum of 14 days of insulin pump data to demonstrate pump use compliance

9. Participant is willing to perform frequent (4 times per day or more) self-monitoring of blood glucose (SMBG), including before meals and before bed, and using a meter and test strips provided by the sponsor during the two weeks of active treatment. This includes participants who are currently using real-time continuous glucose monitoring and may continue to do so, but must also collect SMBG values as instructed.
10. Participant is willing to perform serum ketone measurements whenever the blood glucose is determined to be greater than 250 mg/dL after extended fasting (e.g. overnight or more than five hours after a meal) using a ketone meter and strips provided by the sponsor
11. Participant has BMI in the range 20 – 35 kg/m² inclusive
12. Participant has experience infusing a rapid-acting insulin analog for at least 6 months
13. Participant has been using or is willing to use CGM (reading data available for at least 80% of time for a week of data collection during the screening period). Participants already using Dexcom G6 real time CGM may continue to use their own CGM unit; participants not using the G6 will be provided with a G6 monitor. All participants will be provided with CGM disposables for use during the treatment period.
14. Participant has ability to understand and comply with protocol procedures and to provide informed consent
15. HbA1c ≤8.5%
16. Stable body weight in the 3 months prior to enrollment (change in body weight <5%)

5.3 EXCLUSION CRITERIA

An individual who meets any of the following criteria will be excluded from participation in this study:

- 1) Participants whose average total daily insulin dose exceeds 85 units/day (i.e. typically change insulin reservoirs more often than every 4 days on average)
- 2) Participants who routinely change their commercial insulin infusion sets on average less often than every 4.5 days¹
- 3) Female participant is pregnant or nursing²
- 4) Participant has abnormal skin at intended device infusion sites (existing infection, inflammation, burns, or other extensive scarring)
- 5) Participant has hemoglobin <12.0 g/dL or potassium < 3.5 mEq/L at screening

¹ This will be determined during screening by evaluating the data downloaded from the patient's Medtronic pump. The pump data includes date and time of "cannula prime" events which can be used as surrogate for infusion set change time.

² Documented negative pregnancy test results for female participants required unless participant is menopausal without any spontaneous menstrual cycles for >12 months or key organs have been removed.

- 6) Participant has documented history in last 6 months of severe hypoglycemia associated with cognitive dysfunction sufficiently severe to require third party intervention or a history of impaired awareness of hypoglycemia.
- 7) Participant has a history of diabetic ketoacidosis in the last 6 months
- 8) Participant has known cardiovascular disease considered to be clinically relevant by the investigator
- 9) Participant has known arrhythmias considered to be clinically relevant by the investigator
- 10) Participant has known history of:
 - a) Cushing's Disease,
 - b) pancreatic islet cell tumor, or
 - c) insulinoma
- 11) Participant has:
 - a) Lipodystrophy,
 - b) extensive lipohypertrophy, as assessed by the investigator
- 12) Participant is undergoing current treatment with:
 - a) Systemic oral or intravenous corticosteroids,
 - b) monoamine oxidase (MAO) inhibitors,
 - c) non-selective systemic beta-blockers,
 - d) growth hormone,
 - e) thyroid hormones, unless use has been stable during the past 3 months
 - f) SGLT2 inhibitors
- 13) Participant has significant history of any of the following, that in the opinion of the investigator would compromise the participant's safety or successful study participation:
 - a) Alcoholism,
 - b) drug abuse
- 14) Significant acute or chronic illness, that in the investigator's opinion, might interfere with participant safety or integrity of study results
- 15) Planned operation, MRI or CT which require removal of infusion set or CGM sensor during wear periods
- 16) Current treatment with systemic (oral or IV) corticosteroids, monoamine oxidase (MAO) inhibitors, non-selective beta-blockers, growth hormone, herbal products that, in the opinion of the investigator, may alter insulin sensitivity or confer undue risk to the participant's participation in the study or non-routine vitamins. Furthermore, thyroid hormones are not allowed unless the use of these has been stable during the past 3 months.
- 17) Current participation in another clinical drug or device study
- 18) Inability of the participant to comply with all study procedures or to understand the participant instructions

5.4 STUDY VISIT EXCLUSION CRITERIA

These exclusion criteria should be checked in the evening before each clamp procedure to ensure compliance with study eligibility criteria.

1. Strenuous exercise within the last 24 hours prior to dosing
2. Any medical condition which, in the opinion of the Investigator could interfere with PK and/or glucose metabolism

5.5 LIFESTYLE CONSIDERATIONS

During this study, participants are asked to:

- Refrain from use of analgesics 12 hours prior to pain assessment
- Abstain from alcohol for 24 hours before the start of each clamp
- Refrain from strenuous exercise 24 hours before each clamp
- Refrain from eating a high-carb meal (e.g. Pizza) before admission to the study center
- Keep a diabetes diary provided by the study staff
- Wear a CGM during each 7 day study period provided by the study staff (Dexcom G6®)

5.6 SCREEN FAILURES

Patients who fail screening due to hemoglobin <12.0 g/dL and potassium < 3.5 mEq/L eligibility criteria may be rescreened 1 time up to 2 weeks later.

The site may rescreen one time for A1C >8.5% and/or C-peptide. ≥ 0.6 nmol/L up to 2 weeks after the participant screen failure.

5.7 STRATEGIES FOR RECRUITMENT AND RETENTION

Study participants will be recruited from existing T1DM patient populations already under care for their disease at the study center and via referrals from other diabetes treatment clinics in surrounding areas.

Patients who have had experience with frequent CSII set change outs or who desire to contribute to the evaluation of an extended CSII set will be given the opportunity to participate in the Achilles extended wear feasibility study. This study has been designed as a short (< 30 day) period trial and should not interfere with patient's usual routine, work or social life. Clinical visits and study requirements have been minimized so as to not interfere with daily activities.

Recruitment materials may include written, broadcast and/or internet advertising to facilitate broad patient participation. All recruitment materials shall be submitted to the IRB for review prior to use.

Participants will receive a study stipend for study participation and will be prorated based upon the number of clamps they complete.

6 STUDY INTERVENTION

6.1 STUDY INTERVENTION ADMINISTRATION

6.1.1 STUDY INTERVENTION DESCRIPTION

6.1.1.1 POINT OF ENROLLMENT

Potential patients will be screened for study participation based on the eligibility criteria given in Section 5.1 above. After completing written informed consent, eligible participants shall be assigned a unique

study identifier. Eligible participants will be considered “enrolled” once they signed the informed consent form.

6.1.1.2 SCREENING AND BASELINE (DAY -21 TO DAY -1, VISIT 0)

Participants will be screened and tested to verify study eligibility criteria including a physical exam, complete medical history and laboratory testing. Female participants of child-bearing age, who do not have a documented history of menopause (defined as at least 12 months without menses and/or removal of key organs) must undergo a urine pregnancy test within 7 days of the planned intervention date. All participants must also undergo a urine drug/alcohol screen test, complete blood and metabolic panels within the required screening period (Table 5).

- Patients who fail screening due to hemoglobin <12.0 g/dL and potassium <3.5 mEq/L eligibility criteria may be rescreened for study eligibility 1 time up to 2 weeks later.
- Patients who fail the drug/alcohol screening test may be rescreened for study eligibility one (1) time up to 2 weeks later.

If participants are not currently using and/or are not familiar with the Dexcom G6® CGM sensor, study staff will insert the study sensor during the screening visit and are asked to familiarize themselves with the sensor for 7 days. After one week, CGM data will be downloaded and assessed. If CGM data shows readings for approximately 80% of sensor wear time, the participant may be enrolled in the study. If readings are less than 80%, the participant will be given another week of training. If after the second training period, the threshold of 80% is still not met, the participant is not eligible to participate in the trial.

Participants will be provided with diabetes diaries and a bag of material (see 6.1.1.8) for times spent at home in between study visits to the CRU. Participants will be reminded to fast 12 hours prior to Visit 1 and to avoid a high-carb dinner (e.g. pizza). They are furthermore instructed to refrain from strenuous exercise and alcohol during the 24 hours preceding Visit 1.

Table 5: Screening and Baseline Required Exams

Requirement	Comments
Inclusion criteria	Ensure patients meets all of the inclusion and none of the exclusion criteria
Informed consent	Written consent required by participant
Demographics	Age, gender, race, ethnicity
Medical history	All co-morbidities, prior interventions, Indication for Treatment
Urine Pregnancy test	Female participants of child-bearing potential who are not documented post-menopausal or have undergone extirpation of key organs
Urine Drug/Alcohol Screening	Participants who test positive for drug/alcohol at screening are excluded from study participation. Participants may retest one (1) time within 2 weeks of original test date.
Physical exam	Height, Weight, BMI
Vital Signs	BP, Temperature, Pulse, Respiratory Rate

Concomitant Medications	All prescription and OTC medication and supplement use
CBC	Hgb, HCT, WBC , Differential, Platelet count
C-Peptide	Participants who do not have T1DM as defined in eligibility criteria are excluded
HbA1C	Participants with Hb1AC>8.5% are excluded from study
Basic Metabolic Panel	Sodium, Potassium, Bi-carbonate (also known as carbon dioxide, or CO2), Chloride, BUN, Serum Creatinine *Potassium <3.5 mg/L are excluded
ECG	12 lead ECG required
Participant Training	Insertion site visual inspection, Achilles infusion set change-out, and device return instructions
Study CGM	Insertion and training as needed
Personal CGM	Optional use; if used record Model/Serial number

6.1.1.3 RANDOMIZATION

Participants will be randomized at Visit 1 1:1 to either undergo glucose clamp testing with the Achilles investigational cannula or commercially available control CSII set. If participant is randomized to Achilles cannula in *Treatment Period 1*, they will undergo *Treatment Period 2* with the Teflon control and vice versa. This allows the participant to act as their own control and minimizes user bias. (See section 1.2 for schema.)

After an overnight stay and glucose stabilization, glucose clamp PK/PD experiments will be performed on a Friday, Monday, Wednesday, and Friday schedule, followed by a 2±1 week wash-out period, followed by a second week of glucose clamp PK/PD experiments on a Friday, Monday, Wednesday, and Friday schedule. Alternate days of the week scheduling maybe employed as needed to meet participant and research unit flexibility.

6.1.1.4 OVERNIGHT STABILIZATION

Participants arrive at the clinical site the evening prior to clamp experiment study visits. Site may provide dinner. Participant eligibility will be rechecked (Section 5.4) and those participants eligible to participate will stay onsite overnight. Two intravenous (IV) catheters will be inserted into a peripheral vein, one in each hand/arm: one for blood sample acquisition and one for the infusion of dextrose/insulin. To target a glucose level around 85-115 mg/dL the following morning, participants may be administered insulin at the investigator's discretion by IV infusion using U100 insulin dissolved in saline. Once the IV insulin has been initiated, the participant's insulin pump will be set at a basal rate of 0.1 U/h overnight and throughout the clamp procedure the next day. The concentration of plasma glucose will be determined using a reference analyzer (YSI 2300 Plus) and also by glucose meter/test strips per investigator's discretion. If BG is low, IV infusion of dextrose may be necessary.

A commercial CGM (Dexcom G6) will be inserted into the SC tissue of each study participant using aseptic technique to record the interstitial fluid glucose concentration. The CGM device will be removed by study site personnel at the final clamp day (or sooner if cannula failure has occurred prior to Day 7) during each of the 2 treatment periods.

Food will be withheld (NPO except for water and glucose tablets as needed) for 12 hours prior to and during each glucose clamp experiment. Clamp will take place the following morning.

6.1.1.5 VISIT 1 (FRIDAY)

In the morning, a new infusion set (experimental or control) will be inserted by study personnel, the infusion site will be photographed, and the glucose clamp procedure will be initiated.

The hand/arm used for blood sample acquisition will be gently warmed using a heating pad to produce "arterialized" blood samples. Failure to sample blood from an IV catheter may require insertion of one or more additional IV catheters to complete each 5-hour clamp study.

The reservoir of the insulin pump will be filled with insulin lispro. The reservoir of the participant's pump will be removed and replaced with the insulin prepared by the study personnel. The 23" insulin tubing will be connected to the pump and primed. The infusion set plastic hub will be over-taped with Simpach kinesthesiology tape to further ensure that cannula dislodgement will be unlikely during the treatment period. Areas of lipohypertrophy/lipodystrophy and areas of recent CSII insertion will be avoided. The participant's own commercial infusion set will be removed, and a commercial/investigational cannula will be inserted at an angle of approximately 30 degrees into the subcutaneous tissue of the abdomen using aseptic technique, approximately 3 cm lateral to the midline and, following a cannula prime procedure. The pump immediately started on a constant basal rate of 0.1 U/h which will be maintained throughout the clamp. There should be a suitable insertion site on the contralateral abdomen at approximately the same rostral/caudal level to be used during the second treatment period.

The run-in period should last no longer than 3.5 hours, if BG is not stable after this time, the participant cannot continue in the study and is sent home. He/she may return another day. Once the BG level of approximately 95 ± 15 mg/dL has been maintained for at least 40 minutes (measured every 10 minutes), the IV insulin (dextrose) is discontinued, and the baseline will be recorded for 20 min (blood draw every 5 min). 20 minutes after discontinuation of IV insulin, a SC bolus of lispro insulin (0.15 U/kg) is administered via the pump (t0). Baseline plasma glucose level is defined as mean plasma glucose at time points t-20, t-15, t-10, t-5, and t0. After t0, blood samples for PK analysis are drawn every 3 minutes for 15 min (Clamp Part I), every 5 minutes for 40 minutes (Clamp Part II), every 10 min for 30 min (Clamp Part III), and every 15 minutes for 45 minutes. In the Final Phase, blood is drawn every half an hour until clamp termination at 300 minutes (see Table 6). Up to 15 blood samples will be obtained overnight prior to the day of the glucose clamp procedure, and 8 additional blood samples will be obtained during stabilization on the morning of the clamp procedure prior to administration of the insulin bolus. Blood samples for immediate glucose determination will be drawn every 5 minutes for 60 minutes following insulin bolus, and then every 10 minutes for the remainder of the clamping period at 300 minutes post-bolus. Blood samples will be acquired using aseptic technique and double stopcock technique to minimize blood loss. A maximum of 66 samples (24 x 1.5 mL [for BG and insulin] + 6 x 1.0 mL [for PK only] + 36 x 0.5 mL for BG only = 62.0 mL) will be drawn during the stabilization period and the clamp procedure, resulting in a total blood loss of 248 mL during 4 clamps over each week. Combining both

clamping weeks, this represents less than 1 unit of blood (=525 mL). Blood samples will be centrifuged to plasma, plasma glucose concentration measured, and plasma frozen in 2 aliquots for future measurement of insulin concentration. The detailed clamp sampling schedule is summarized in Table 6.

Table 6. Clamp visit sampling schedule

Phase	Approximate Clock Time (hh:mm)	Nominal Time (min)	No. of samples	Volume/Sample (mL)	Total Volume (mL)
Stabilization, over night			15	0.5	7.5
Baseline Part I	7:00	-60	5	0.5	2.5
	7:10	-50		0.5	
	7:20	-40		0.5	
	7:30	-30		0.5	
	7:40	-20		0.5	
Discontinue IV insulin & Dextrose					
Baseline Part II	7:45	-15	3	1.5	4.5
	7:50	-10		1.5	
	7:55	-5		1.5	
Bolus	8:00	0	1	1.5	1.5
Clamp Part I	8:03	3	7	1	6.5
	8:05	5		0.5	
	8:06	6		1	
	8:09	9		1	
	8:10	10		0.5	
	8:12	12		1	
	8:15	15		1.5	
Clamp Part II	8:20	20	9	1.5	13.5
	8:25	25		1.5	
	8:30	30		1.5	
	8:35	35		1.5	
	8:40	40		1.5	
	8:45	45		1.5	
	8:50	50		1.5	
	8:55	55		1.5	
	9:00	60		1.5	
Clamp Part III	9:10	70	3	1.5	4.5
	9:20	80		1.5	
	9:30	90		1.5	
Clamp Part IV	9:40	100	10	0.5	8.0
	9:45	105		1	

Phase	Approximate Clock Time (hh:mm)	Nominal Time (min)	No. of samples	Volume/Sample (mL)	Total Volume (mL)
	9:50	110		0.5	
	10:00	120		1.5	
	10:10	130		0.5	
	10:15	135		1	
	10:20	140		0.5	
	10:30	150		1.5	
	10:40	160		0.5	
	10:50	170		0.5	
	11:00	180		1.5	
	11:10	190		0.5	
	11:20	200		0.5	
	11:30	210		1.5	
	11:40	220		0.5	
	11:50	230		0.5	
Final Phase	12:00	240	13	1.5	11.5
	12:10	250		0.5	
	12:20	260		0.5	
	12:30	270		1.5	
	12:40	280		0.5	
	12:50	290		0.5	
	13:00	300		1.5	
Observation at site			66 total samples		
				Total volume per clamp =	62.0 mL

During the 5-hour clamp plasma glucose concentration will be maintained at 95 ± 15 mg/dL with IV infusion of dextrose (0.1 to 4 mg/kg/min), titrated using a computerized dosing algorithm according to frequent BG measurements. The trigger plasma glucose concentration for onset of glucose infusion will be a value that is 5 mg/dL below the mean obtained during Baseline Part II (i.e. -15, -10 and -5 minutes before bolus delivery at T=0). The dosing calculator will be used to determine the optimal glucose infusion rate (GIR) for each subsequent time period between BG measurements. If insulin is infused, glucose infusion must be stopped and vice versa. The dextrose infusion rate will be increased to match insulin lispro's glucose lowering effect over time until the glucose lowering effect of the insulin lispro bolus reaches baseline (i.e. glucose infusion rate of 0) or 5 hours after bolus administration.

In the case of persistent hyperglycemia (BG > 250 mg/dL) over 30 minutes without dextrose infusion, the clamp will be terminated early. A correction bolus will be given via the pump and the BG measured to determine whether BG was lowered by 50 mg/dL within 1 hour. If this is not the case, the CSII catheter is

considered failed, a new fresh commercial insulin infusion set inserted and another bolus is given. Patients will stay at the CRU until they have finished their meal and their BG has dropped as assessed by two blood glucose meter measurements in the range of 90 – 200 mg/dL separated by at least 30 minutes.

The study participant will be provided with a meal at the conclusion of the clamp visit. Insulin lispro will be infused through the study investigational or commercial CSII catheter using the participant's typical basal/bolus pattern of delivery during home care between study visits. Study personnel will call the participant the same evening to ensure the participant's wellbeing.

6.1.1.6 VISITS 2, 3, AND 4

Participants arrive the prior evening for stabilization and procedures explained above in section "Visit 1" are repeated (except insertion of CSII catheters). If CGM failed, a new CGM will be inserted by trained study staff.

If the CSII catheter does not fail before day 7, the investigational/commercial CSII set will be removed upon completion of the clamp experiment on Visit 4A/Visit 4B. The site and cannula will be photographed, and the cannula inspected under a microscope. A fresh CSII catheter (as routinely used by the participant) will be inserted at a different site, the pump connected, and routine glycemic management resumed. The change-out will be documented in the appropriate source documents and CRF.

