4.3 JUSTIFICATION FOR DOSE

A bolus of commercial U-100 insulin lispro (0.15 units/kg) will be infused through an investigational or commercial infusion set into the SC tissue of the abdomen at time zero (t0 on DOI and on Days 3,5 and 7) of each glucose clamp PK/PD study using a Medtronic pump. The concentration of BG will be maintained approximately in the 95±15 mg/dL range using an IV infusion of 20% dextrose and/or insulin infusion.. The IV dose may range from 0.1 to 3.0 units/h depending on the patient's regular basal rate.

This insulin lispro bolus dose (0.15 units/kg) is slightly higher than a typical dose used to cover an average sized meal for a T1DM patient with an average insulin/carbohydrate ratio

(0.15 units/kg x 70 kg = 10.5 units). The majority of the published PK/PD studies utilized a 0.15 unit/kg bolus dose, some used a 0.20 units/kg bolus dose, and a few studies used a 0.10 or 0.12 unit/kg dose.

Insulin lispro will be infused through the same investigational or commercial insulin infusion set after each glucose clamp (or until CSII failure) using a Medtronic insulin pump and a basal/bolus pattern of delivery. The basal infusion rate, meal bolus dose and correction dose will be adjusted by each study patient according to their routine clinical methods [SMBG glucose measurements, CGM glucose measurement (if available), insulin to carbohydrate ratio, meal size and meal composition]. Study participants requiring a large daily insulin dose may require a change out of their pump reservoir with fresh insulin as needed during each treatment period.

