4.3.2.3.3 AUC_{0-t}

The AUC_{0-t} of GIR over wear time will be calculated using trapezoid rule and the actual time points. Missing data for the calculation of the AUC will be handled as followed:

1. If the reading for Time 0 is missing, it will be the average of up to 3 prior readings. However, if there is no prior readings available, it will be assumed to be 0
2. If the reading at (actual) time t ($t < 300$ min) is missing, it will be imputed with linear interpolation
3. If the reading at $t=300$ min is missing:
 - a. The reading at $t=300$ min will be imputed using the regression line obtained when estimate λ (section 4.3.2.3.1).
 - b. If λ is missing, AUC_{0-t} will be set as missing.

4.3.2.3.4 $AUC_{0-\infty}$

$AUC_{0-\infty}$ is estimated as

$$AUC_{0-\infty} = AUC_{0-last} + AUC_{last}, \text{ where } AUC_{last} = GIR_{last}/\lambda$$

If λ is missing, then $AUC_{0-\infty}$ is set as missing.

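### The protocol leaves open whether IV insulin may run after the test bolus, and the SAP has no rule for clamps in which it did

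*Protocol*

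**What the plan says.** **Before the bolus.** Protocol 6.1.1.5 requires at least 40 minutes of steady glucose, after which "the IV insulin (dextrose) is discontinued, and the baseline will be recorded for 20 min". The bolus follows at t0. Table 6 repeats the stop in a row between the -20 and -15 minute samples: "Discontinue IV insulin & Dextrose". From then on the only planned background insulin is the pump basal of 0.1 U/h through the set under test.

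**After the bolus.** The paragraph below Table 6 opens with "During the 5-hour clamp plasma glucose concentration will be maintained at 95 ± 15 mg/dL with IV infusion of dextrose". It then describes the dosing calculator and adds: "If insulin is infused, glucose infusion must be stopped and vice versa". If glucose stays above 250 mg/dL for over 30 minutes without dextrose, the clamp ends, a correction bolus goes through the pump, and the set counts as failed if glucose does not fall by 50 mg/dL within an hour.

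**Section 4.3.** Directly after describing the bolus at t0, it has glucose held in the 95±15 mg/dL "range using an IV infusion of 20% dextrose and/or insulin infusion". The IV dose is given as 0.1 to 3.0 units/h, depending on the participant's basal rate.

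**SAP.** Under 4.3.2.3.3 the AUC "of GIR over wear time will be calculated using trapezoid rule and the actual time points". Insulin AUCs are computed the same way (4.3.2.5.1, 4.3.2.5.3). The baseline-adjusted versions (4.3.2.3.5, 4.3.2.5.2) subtract the time-0 value multiplied by t. Profiles that are zero throughout are removed from all analyses (4.3.2.2). IV insulin is not mentioned.

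**The concern.** The trial reads set performance from what happens after t0, on the premise that the insulin acting then came through the set. IV insulin given after t0 breaks that premise. Its use would also not be random. Dextrose cannot lower glucose, so the situation in which staff might turn to insulin is glucose above target with dextrose already off, and poor absorption from the cannula makes that situation more likely. The co-intervention would then depend on the outcome being measured, and could differ by set and by wear day.

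Three results are exposed: the PK parameters, the primary slope of ln(AUC0-300 GIR), and the detection of a failed set during a clamp. As far as the two documents show, no one is asked to record post-bolus IV insulin for analysis, so a reader of the results could not tell which clamps were affected.

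**Working it through.** **1. The passages side by side**

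| Place | Period described | IV insulin |
|---|---|---|
| Protocol 6.1.1.5, text | Run-in to t0 | Stopped 20 min before the bolus |
| Protocol Table 6 | Between -20 and -15 min | Stopped, with dextrose |
| Protocol 6.1.1.5, below Table 6 | The 5-hour clamp | Dextrose is the named agent; insulin appears conditionally |
| Protocol 4.3 | Follows the t0 bolus; no period stated | Dextrose and/or insulin, 0.1 to 3.0 U/h |

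The first two rows close IV insulin before t0. The last two leave it open, and no sentence ranks them.

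**2. Does the SAP's baseline adjustment deal with it?** Adjusted AUC = AUC(0-t) - GIR(0) × t. If dextrose is off from -20 min as stated, GIR(0) = 0, and the 300-minute adjustment is 0 × 300 = 0. For insulin, the amount subtracted is fixed by the time-0 concentration. Neither can remove insulin started later.

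**3. PK scale.** The plan's own bolus figure reproduces: 0.15 × 70 kg = 10.5 U. Taking the range in 4.3 as an assumption:
- One hour: 0.1 to 3.0 U. 0.1/10.5 = 1%; 3.0/10.5 = 29%.
- Five hours: 0.5 to 15 U. 0.5/10.5 = 5%; 15/10.5 = 143%.

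These are dose ratios, not forecasts. They carry over to insulin AUC only if exposure is proportional to dose and the assay reads the IV insulin. The protocol names neither the IV analog (6.1.1.4) nor the specificity of the radioimmunoassay (8.2).

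**4. Direction for GIR**
- While insulin runs, dextrose must be off, so GIR is 0.
- After insulin stops, its residual action may call for dextrose, which raises GIR.
- A profile that would have been zero throughout is dropped under SAP 4.3.2.2. A few positive readings caused by IV insulin would keep it in with a very low AUC, which makes that set look worse.

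**5. What a change in one clamp does to the slope.** Days 0, 3, 5, 7 have mean 3.75 and Sxx = 14.0625 + 0.5625 + 1.5625 + 10.5625 = 26.75. The day-7 least-squares weight is 3.25/26.75 = 0.1215. If IV insulin multiplies one participant's day-7 GIR AUC by f, that participant's slope moves by 0.1215 × ln f. If seven participants contribute complete data, the mean slope for that set moves by one seventh of this. The values of f are assumptions.

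| f | Participant's slope, per day | Mean of seven, per day |
|---|---|---|
| 1.2 | +0.022 | +0.003 |
| 0.8 | -0.027 | -0.004 |
| 0.1 | -0.280 | -0.040 |

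The design difference is 0.07 per day. Moderate distortion of one clamp matters little. On the log scale, a near-zero profile kept in matters a good deal.

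**6. Set failure.** IV insulin could hold glucose below 250 mg/dL, and the termination and correction-bolus check would then not be reached.

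**The case against.** The best case on the other side is that the procedure is clear enough. The stop is stated twice. The sentence that governs the 5-hour clamp names only dextrose. The insulin clause is conditional and reads as a rule against running both. The rate range in 4.3 is tied to the basal rate, which fits replacement overnight and during run-in. The stated response to persistent hyperglycemia is to end the clamp and bolus through the pump. Set failure has other routes in Protocol 7.1.1, such as occlusion alarms and site inflammation, which IV insulin does not touch. The study also stopped after its seventh completer, so a new log field would come too late.

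Most of this stands, and it rules out three stronger readings.
- A reader might infer that the protocol directs IV insulin once glucose passes the upper target. It does not; it permits insulin conditionally or by omission.
- A reader might infer that a failing set would look preserved on the primary endpoint. The documents do not support that: GIR is 0 while insulin runs, and step 4 shows effects in both directions.
- A reader might convert the roughly 21% day-7 loss of insulin AUC cited in Protocol 2.2.3 into a slope and compare it with 0.07. The first is insulin exposure over 4 hours and the second is a difference in ln(GIR AUC), so the ratio does not measure bias in the primary endpoint. A set with that loss would still deliver the equivalent of 0.79 × 10.5 = 8.3 U, and nothing in the documents implies hours of IV insulin in that case.

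The objection does not close the gap. The insulin clause sits inside the post-bolus paragraph, 4.3 follows the t0 bolus without limiting itself to the run-in, and the SAP is silent.

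**Conclusion.** The concern holds as an unresolved ambiguity in the protocol joined to a missing analysis rule. If IV insulin ran after t0 in any clamp, following the SAP would credit it to the set in insulin AUC and MRT, to the extent the assay reads it. GIR in that clamp would not be a measure of the SC bolus alone, with net direction uncertain, and one of several routes to a failure call could be missed.

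The overall size cannot be derived, because the documents give neither the frequency nor the dose of post-bolus IV insulin. The figures above show scale only, and the PK ratios also assume that the range in 4.3 applies after t0, which is itself in doubt. If no clamp had such insulin, the results are unaffected, but that needs to be shown. With about seven completers, a single affected clamp carries more weight than it would have with 24.

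**What to change.** 1. **Reconcile the text.** Bring Protocol 4.3, the run-in text with Table 6, and the clamp paragraph of 6.1.1.5 into one statement on IV insulin after t0. Which rule it should be is for the sponsor and investigator.
2. **Retrieve and report.** From source records, obtain start, stop and rate of any IV insulin after -20 minutes for every clamp. Report affected clamps by set and day, including a count of none.
3. **PK rule in SAP 4.3.2.5.** Samples taken after the start of post-t0 IV insulin are not used in PK parameters attributed to the set. State that the interpolation and 300-minute regression rules of 4.3.2.3.3 do not refill them. Parameters that need only earlier samples can be kept.
4. **Primary contrast, SAP 4.4.4.1.** Keep the planned analysis. Add a sensitivity analysis that either excludes affected clamps or treats them as non-response with a stated small positive AUC. Setting GIR to 0 is not workable: it can create all-zero profiles, which 4.3.2.2 removes, and ln(0) is undefined. Because the f = 0.1 row shows how strongly a low value pulls the slope, fix the value in advance and show at least one alternative.

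**Cost.** A clarification, a review of clamp records and a short SAP paragraph. Some PK parameters are lost for affected clamps, and that loss is itself related to poor absorption, so the counts by set must stand next to the PK results.
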